In healthy, young volunteers, subjected to an oral glucose tolerance curve of 180 minutes, acute or chronic exposure to 48 - 96 mg of sucralose in a single dose or 10 weeks daily intake, respectively, causes an increase in the average levels of the area under the curve of insulin, glucose and other intolerance to this carbohydrate markers when compared with water as a placebo.

Principal outcome

To evaluate the effect of acute and chronic exposure to 48 - 96 mg of sucralose in a single dose or for 10 weeks, respectively, on the average levels of the area under

the insulin curve in healthy, young volunteers, subjected to an oral glucose tolerance curve at 180 minutes, in a randomized, double-blind, placebo-controlled study.

Materials and Methods

This is a randomized, double-blind, placebo-controlled trial in young and healthy adults, the study at the General Hospital of Mexico, [name] from April 2016 to June 2018, and the present study meets with the criteria of CONSORT.

To evaluate the acute effect of sucralose, the experimental groups will receive 48 mg / 60 ml and 96 mg / 60 ml of fasting sucralose in a single shot, while the control group will receive 60 ml of water as a placebo, before undergoing a CTOG with 75 g of glucose during 180 min. During this procedure, 4 ml of blood will be taken at -15 (sucralose intake or placebo) and 0 (75 g glucose intake) as a base and then at 15, 30, 45, 60, 75, 90, 105, 120 and 180 minutes post-load glucose for the quantification of insulin, glucose, C-peptide, glucagon, GLP-1, and GPI levels. Subsequently, to evaluate the chronic effect of sucralose, the experimental group will continue with the daily intake of 48 – 96 mg / 60ml of sucralose for 10 consecutive weeks, while the control group will receive 30 ml of water daily as a placebo during the same period of time. At the end of 10 weeks of treatment with sucralose or placebo, a second CTOG (75g / 180 min) will be carried out, taking again 4 ml of blood at -15 and time zero, and subsequently 4 ml at 15, 30, 45, 60, 75, 90, 105, 120 and 180 minutes after glucose loading. To evaluate the acute exposure to the sweetener, the area under the curve (AUC) of the blood glucose levels obtained during the CTOG in each participant will be calculated and the average differences

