between the sucralose groups versus placebo will be compared, adjusting for BMI. In the case of chronic exposure to the sweetener, the AUC values between the sucralose groups versus placebo will be compared after 10 weeks, and the AUC values will be compared at the beginning and end of the study in the group that received sucralose, adjusting in both cases for BMI. In addition to the determination of glucose levels during the two CTOGs, the circulating levels of insulin, glucagon, C peptide, GIP, GLP-1, TNF- α , pCr, IFN- γ , IL-1 β , IL-4, IL-6, IL-10, IL-12, IL-13, IL-17, IL-23, and inflammatory monocytes CD14hiCD16 + CD11c + CCR2hiCX3CR1lowCD206-, with the purpose of comparing their values in the acute exposure scheme and chronic to sucralose, adjusting for BMI. The samples of excrement from acute and chronic exposure will be processed to extract the DNA and run them in PCR in real time and the percentage of each bacteria present in feces will be compared at the beginning and at the end. The difference between the two samples will be analyzed by means of square chi.

Ethical considerations

This study will be carried out in compliance with the guidelines of the protocol, with the ethical principles of the Declaration of Helsinki in its most recent version approved during the 64th Assembly of the World Association of Physicians, in Fortaleza Brazil, in October 2013, in accordance to the principles that govern human research in the General Health Law and in accordance with the ethical and research guidelines of the General Hospital of Mexico "[name].

REFERENCES

3. Garcia LM, da Silva KS, Del Duca GF, da Costa FF, Nahas MV. Sedentary behaviors, leisure-time physical inactivity, and chronic diseases in Brazilian workers: a cross sectional study. *J Phys Act Health.* 2014;11(8):1622-34.

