Statistical Analysis Plan

México CDMX. January 20th 2016

Effect of Acute or Chronic Ingestion of Sucralose on Serum Insulin in Young and Healthy Adults: A Randomized, Double-Blind, Placebo-Controlled Trial.

The statistical analysis will help us to provide accurate and quantifiable data in order to increase the documented information about the sucralose; this analysis will also help us to have a better reliability on the study results.

Estimation of sample size

Considering the results on the difference of the averages of the areas under the curve for plasma insulin in obese volunteers exposed to sucralose and water, before an oral glucose load, as reported by Pepino et al., [1], the estimation of the Sample size was:

t tests - Means: Difference between two independent means (two groups)

Analysis: A priori: Compute required sample size

Input:

Tail(s)	=	One
Effect size d	=	0.419231264
α err prob	=	0.05
Power (1- β err prob)	=	0.8
Allocation ratio N2/N1	=	1

Output:

Noncentrality parameter δ	=	2.5153876
Critical t	=	1.6556552
Df	=	142
Sample size group 1	=	72
Sample size group 2	=	72
Total sample size	=	144
Actual power	=	0.8046976

For the estimation of the sample size the program GPower version 3.1.9.2 (University of Düsseldorf, Germany) was used. The difference between two

averages was estimated by means of a test of t, of an address, with an alpha value (0.05), assuming unequal variances, for a power of proof of 80%, a value of Cohen of 0.419231264, the sample size is 72 volunteers per group, the total sample size is left in 144 volunteers.

The demographic analysis will be assessed with descriptive statistics, ensuring the two groups are balanced in their moments for the main variables.

The statistical analysis of the presence or occurrence of any inflammatory process during the the study will be carried out by comparing the before / after differences between the sucralose and water groups for the whole sample, adjusting for BMI, these differences will be compared for each analyte related to chronic inflammation such as C-reactive protein, tumor necrosis factor-alpha, interleukin (IL) 6, IL-12, IL-10 and inflammatory monocytes CD11c + CCR2High.

In order to calculate the area under the glucose tolerance test curve will be assessed using the trapezium method [2] for glucose, insulin, C-peptide, glucagon GPI and GLP-1.

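### Inflammation analysis: no marker scale is stated and no acute illness is recorded at the two visits, so a modest sucralose effect could be lost in noise

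*SAP*

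**What the plan says.** The SAP's paragraph on inflammation states that the analysis of the "presence or occurrence of any inflammatory process during the the study will be carried out by comparing the before / after differences". The contrast is sucralose against water in all participants, with BMI as the only covariate. The comparison is made "for each analyte related to chronic inflammation such as C-reactive protein, tumor necrosis factor-alpha, interleukin (IL) 6, IL-12, IL-10" and for inflammatory monocytes. It names no scale, transformation or test, no rule for extreme values and no sensitivity analysis.

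The protocol (Materials and Methods) places these measurements at the two glucose tolerance tests: "In addition to the determination of glucose levels during the two CTOGs, the circulating levels of insulin" and the other markers are determined "with the purpose of comparing their values in the acute exposure scheme and chronic to sucralose, adjusting for BMI". The visits are 10 weeks apart: "At the end of 10 weeks of treatment with sucralose or placebo, a second CTOG" is carried out.

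The only statement about participants' health is the design sentence: "This is a randomized, double-blind, placebo-controlled trial in young and healthy adults". That describes who is recruited, not their state on the day of the second test. Neither document mentions a check for infection, injury or vaccination at a visit, a record of anti-inflammatory or antibiotic use, or a rule for samples taken during an illness.

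**The concern.** Whether sucralose causes a systemic inflammatory state is part of the protocol's rationale (Background), and interleukins appear in its aim. The analysis rests on one difference per person between two days. CRP and several cytokines are right-skewed and can rise many-fold in a common infection. On an untransformed scale, a few such values set the standard deviation of the differences. A low-grade sucralose effect would then probably be missed, and the null result could be read as reassurance.

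The stated target is also wider than the data. Two sampling days show change between those days. They cannot show whether an inflammatory process came and went in the 10 weeks between.

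**Working it through.** **1. The plan's own figure.** The documents give no power figure for inflammation. The stated sample size concerns insulin AUC and supplies only the arm size used here. With d = 0.419231264 and 72 per group, the noncentrality is 0.419231264 × √(72/2) = 2.5154. The one-sided 5% critical t on 142 df is 1.6557 and power is 0.8047. All three match the SAP.

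**2. Inputs.** From the SAP: 72 per arm, two arms, before/after differences, alpha 0.05. Assumed, because the documents give no marker data: resting CRP lognormal with median 1 mg/L and log SD 1.0; between-visit log correlation 0.6; a true 50% rise on sucralose at week 10; 1% or 2% of visits, independent of arm, showing 20 or 40 mg/L. At 2%, that is 144 × 0.02 = 2.88 people per visit. Tests are two-sided.

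**3. Check by formula, no illness.**
- Log scale: SD of the difference = √(2 × (1 − 0.6)) = 0.894. SE = 0.894 × √(2/72) = 0.149. Effect ln 1.5 = 0.405, so z = 2.72 and power is about Φ(2.72 − 1.96) = 0.78.
- Raw scale: the lognormal mean is exp(0.5) = 1.65, so the effect is 0.5 × 1.65 = 0.82 mg/L. Visit variance is e(e − 1) = 4.67 and covariance is e(e^0.6 − 1) = 2.23. The variance of the difference is 2 × (4.67 − 2.23) = 4.87 on water and 4.67 × (1 + 2.25) − 2 × 1.5 × 2.23 = 8.5 on sucralose. SE = √((4.87 + 8.5)/72) = 0.43 and z = 1.9, so power is about one half.

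**4. Simulation (at least 3,000 trials per scenario; Monte Carlo SE about 0.01).** Power for the assumed 50% rise:

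| Visits ill, level | Raw differences | Log differences |
|---|---|---|
| none | 0.53 | 0.76 |
| 1%, 20 mg/L | 0.30 | 0.68 |
| 1%, 40 mg/L | 0.18 | 0.64 |
| 2%, 20 mg/L | 0.20 | 0.61 |
| 2%, 40 mg/L | 0.10 | 0.55 |

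Excluding people ill at either visit gives 0.75 to 0.77 on the log scale and about 0.53 on the raw scale. The raw SD of the difference rises from about 2.5 mg/L to between 3.5 and 7.7 mg/L.

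**5. Other inputs.** With median 0.8 mg/L, log SD 0.9, and infections adding a median 20 mg/L at 2% of visits, raw power falls from 0.69 to 0.11. Log power falls from 0.85 to 0.65 and returns to 0.85 with exclusion.

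**6. False positives.** With no sucralose effect, the raw rejection rate stays at 0.04 to 0.05 in every scenario of step 4 (0.02 to 0.05 raw and 0.04 to 0.06 log under the inputs of step 5). The reason is simple. If k similar outliers of height H fall in one arm of n and dominate, the mean shifts by kH/n and its SE is about √k × H/n, so t is about √k. One outlier gives 1.0 and two give 1.4, both below 1.656.

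**7. The estimate.** One person at 40 mg/L moves an arm mean by about (40 − 1.65)/72 = 0.53 mg/L, against a true effect of 0.82 mg/L. At 2% of visits and 40 mg/L, the raw estimate pointed the wrong way in 28% of trials, against 2% with no illness.

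**8. Baseline adjustment.** On the log scale without illness, a difference has variance 2 × (1 − 0.6) = 0.80. Week 10 adjusted for baseline has residual variance 1 − 0.6² = 0.64, which is 20% lower.

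**The case against.** **The SAP does not say raw.** A reader might infer that it prescribes untransformed differences. It names no scale, so untransformed is only the default reading. This stands: the defect is that the scale is unspecified.

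**Most of the loss comes from the scale.** Log differences with no illness check (0.55 to 0.68), or a rank test on the differences (0.66 to 0.69 with illness), beat raw differences with every ill participant removed (about 0.53). This also stands, and it puts the analysis scale first in the fix. Illness still costs power on the log scale, and recording it recovers nearly all of that loss.

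**Infections could be mistaken for a sucralose effect.** A reader might infer that a chance imbalance of one or two infections would read as sucralose causing or preventing inflammation. The documents do not support this. The arms are randomized and double-blind, so infections are non-differential on average, and they inflate the standard error along with the mean. The false-positive rate does not rise. A single trial's estimate can shift by chance, but its interval widens accordingly.

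**Reach and inputs.** The principal outcome, insulin AUC, is not affected. The CRP inputs are assumptions, and no cytokine or monocyte was modelled. The protocol is brief throughout, so the missing illness check is an omission and not evidence of a deliberate choice. These limits are accepted.

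**Conclusion.** The point holds as a loss of precision in a secondary analysis that serves a stated aim. If the differences are analysed untransformed, as a literal reading allows, power for an assumed 50% CRP rise falls from 0.53 to between 0.10 and 0.30 when 1–2% of visits coincide with an illness. On the log scale it falls from 0.76 to between 0.55 and 0.68, and is 0.75 to 0.77 with ill samples excluded.

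The likely harm is a falsely reassuring null or a noisy estimate. It is not a systematic false sucralose effect, since type I error is not inflated.

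The absolute figures depend on the assumed CRP distribution, correlation, effect and illness rate. Correlation and effect size were not varied. The ordering (raw worst, log better, log with exclusion best) was the same under both sets of inputs. The calculation uses the SAP's two arms of 72. The protocol describes two sucralose doses plus water, so the actual contrasts may be smaller.

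**What to change.** **In the SAP.** Analyse each marker at week 10 on the log scale by ANCOVA, with the log baseline value and BMI as covariates. Pre-specify a sensitivity analysis that excludes flagged samples. Reword the objective as change between the two visits, since two samples cannot establish what happened throughout the study.

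**At both visits.** Record recent infection, injury, vaccination, and anti-inflammatory or antibiotic use. Fix the rule that flags a sample before unblinding, and report illness by arm.

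**Cost.** A short checklist at two existing visits, some SAP wording, and a few samples dropped from the sensitivity analysis. Arms, assays and sample size do not change. Illness not recorded at the visit is hard to reconstruct later. Whether a visit may be postponed, and what happens to the daily drink in that case, is for the sponsor to decide.

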The statistical analysis of the oral glucose tolerance curves will be carried out by means of an analysis of variance test for repeated measurements and for the area under the curve of each of the metabolic analytes.

For each of the differences between the area under the initial and final curve of glucose, insulin, C-peptide, glucagon, GPI and GLP-1 between sucralose and water, an ANCOVA will be made, taking the BMI as a covariate.

For the analysis of the behavior of the intestinal microbiota, a comparison of the percentages of the flora between the first and the last sample of excrement will be carried out, and a chi square test will be applied.

The correlation between the initial HOMA-IR value and the glucosylated hemoglobin will be explored.

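### Inflammation markers are compared as before/after differences adjusted for BMI alone; leaving out each marker's own baseline costs precision and lets chance imbalance into the estimate

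*SAP*

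**What the plan says.** The SAP paragraph on inflammation, which follows the sample-size section, sets the analysis as "comparing the before / after differences between the sucralose and water groups for the whole sample, adjusting for BMI". It applies this marker by marker: "these differences will be compared for each analyte related to chronic inflammation such as C-reactive protein, tumor necrosis factor-alpha", then IL-6, IL-12, IL-10 and a monocyte subset.

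The protocol (Materials and Methods) lists these and further markers. It ties them to both glucose tolerance tests ("In addition to the determination of glucose levels during the two CTOGs, the circulating levels of insulin" opens the list) and states the aim as "with the purpose of comparing their values in the acute exposure scheme and chronic to sucralose, adjusting for BMI". BMI is again the only adjustment.

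The one ANCOVA that the SAP names, for the differences between initial and final AUC of the metabolic analytes, follows the same pattern: "an ANCOVA will be made, taking the BMI as a covariate".

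Neither document enters the baseline value of the outcome in any model. Neither gives a sampling minute for the inflammation markers. The protocol's times, including the two baseline times ("sucralose intake or placebo) and 0 (75 g glucose intake) as a base"), are stated for the metabolic analytes only.

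**The concern.** A change score is negatively related to its own baseline. People who start high by chance tend to fall, and people who start low tend to rise. If the arms differ at baseline by chance, part of that difference reappears, with opposite sign, in the comparison of changes. Putting the baseline in the model removes this and also reduces the residual variance. BMI does neither job unless it predicts the change itself.

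Whether sucralose provokes systemic inflammation is one of the questions raised in the protocol's Background, and interleukins appear in its aim. The sample size was set on insulin AUC alone, so the markers have no power calculation of their own. An avoidably wide confidence interval around a null result could be taken as reassurance.

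**Working it through.** **1. The plan's own figure.** The inputs from the SAP sample-size section are d = 0.419231264, 72 per group, and a one-sided t test ("by means of a test of t, of an address") "with an alpha value (0.05), assuming unequal variances, for a power of proof of 80" per cent. The noncentrality is d × √(n/2) = 0.419231264 × √36 = 2.5153876. The critical t on 142 df is 1.6556552, and the power is 0.8046976. All three match the SAP. This figure concerns insulin AUC; none is given for the inflammation markers.

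**2. Variances.** Assume equal SDs (set to 1) before and after, with correlation r.

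- Change score: 1 + 1 − 2r = 2(1−r).
- Baseline as covariate: 1 − r².
- Ratio: (1−r)(1+r) / [2(1−r)] = (1+r)/2.

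The documents do not give r, so a range is assumed. The sample size for equal precision is 72 × (1+r)/2. Power is illustrative only: it takes a true difference of 0.419 SD of the follow-up value, 72 per group and one-sided 0.05, with noncentrality 2.5154/√variance.

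| r | Change score 2(1−r) | With baseline 1−r² | Ratio | n per group for equal precision | Power, change | Power, with baseline |
|---|---|---|---|---|---|---|
| 0.3 | 1.40 | 0.91 | 0.65 | about 47 | 0.68 | 0.84 |
| 0.5 | 1.00 | 0.75 | 0.75 | 54 | 0.80 | 0.89 |
| 0.7 | 0.60 | 0.51 | 0.85 | about 61 | 0.94 | 0.97 |
| 0.9 | 0.20 | 0.19 | 0.95 | about 68 | about 1.00 | about 1.00 |

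Below r = 0.5 the change score has variance above 1, so it is then less precise than comparing follow-up values with no baseline at all.

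**3. Does BMI stand in for the baseline?** If BMI correlates equally (b) with the marker at both times, its covariance with the change is b − b = 0, so it explains none of the change. In a simulation of 10,000 trials per r (72 per group, BMI in both models, b = 0.3 assumed), the variance ratios were 0.62, 0.73, 0.84 and 0.95 at r = 0.3, 0.5, 0.7 and 0.9. BMI therefore does not take the place of the baseline.

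**4. Chance imbalance.** The expected shift of the BMI-adjusted change estimate is −(1−r) per SD of baseline imbalance. The simulated slopes were −0.70, −0.50, −0.31 and −0.10. With the baseline added they lay between −0.008 and 0.003. For scale, one standard error of the baseline difference is √(2/72) = 0.167 SD. An imbalance of 0.2 SD at r = 0.5 shifts the estimate by 0.5 × 0.2 = 0.10 SD, and 0.10/0.419 = 0.24, about a quarter of the effect the trial was sized on.

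**5. Average bias.** Over all simulated randomisations both analyses centred on the true 0.419 (means 0.417 to 0.422).

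**The case against.** The strongest reply is that BMI-adjusted change is a legitimate analysis and that nothing here makes it invalid. That stands. A reader might infer that regression to the mean biases the planned comparison. The documents do not support this: the trial is randomised, so regression to the mean is the same in both arms in expectation. What the baseline covariate removes is its effect through chance imbalance in the trial actually run.

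Four further points limit the claim.

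- **Size.** No correlation is given. A reader who looked only at r from 0.3 to 0.7 would infer a saving of 15% to 35%, but at r = 0.9 it is 5%.
- **A change score is never more precise.** This is too absolute. It needs equal baseline slopes or 1:1 allocation. The SAP sizes two equal groups, but the protocol describes two sucralose doses and placebo, and pooling the doses could give unequal groups. A simulation with 2:1 allocation and assumed slopes of 1.1 (water) and 0.6 (sucralose) gave common-slope ANCOVA 6% more variance than the change score. That case is extreme; slopes of 0.9 and 0.5 still favoured ANCOVA.
- **A baseline before intake.** It is tempting to assume that one exists. A *before* value must exist, but no sampling time is stated for these markers. For the metabolic analytes the protocol counts time 0 as a base, and that is 15 minutes after intake. A covariate measured after intake could itself be affected by treatment.
- **Rank.** The principal outcome is insulin AUC, and the hypothesis does not name inflammation.

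These points trim the claim. None is a reason to leave the baseline out.

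**Conclusion.** The point holds as one of precision and of robustness to chance imbalance, not of validity. The direction is secure under 1:1 allocation or equal slopes. The size depends on an unknown r: the variance of the arm difference falls by 35%, 25%, 15% or 5% at r = 0.3, 0.5, 0.7 or 0.9, assuming equal variances before and after. For skewed markers the linear adjustment may need a log scale; the documents give no distributions, so this too is an assumption.

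The ANCOVA of AUC differences, which covers the principal outcome, omits the starting value in the same way and should be changed with it. One caution applies there. By the protocol's schedule the first tolerance test follows the first intake by 15 minutes, so the initial AUC is not a value from before intake. Adjusting for it and subtracting it agree on average only if the single dose leaves that AUC unchanged or the slope on it is 1.

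**What to change.** Keep the comparison and BMI, and replace the SAP sentence with wording such as:

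> For each inflammatory marker, the post-exposure value (or equivalently its change from baseline) is compared between sucralose and water by ANCOVA with the baseline value of the same marker and baseline BMI as covariates, for each exposure scheme (acute, chronic) in which the marker is compared. Baseline is the sample taken before the first sucralose or placebo intake.

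With baseline in the model, the change and the post-exposure value give the same treatment estimate, so the planned outcome need not be dropped. Naming both schemes matters: a sentence confined to week 10 would leave the protocol's acute marker comparison without an analysis.

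Add the starting value to the AUC ANCOVA in the same way, and say there which value is used, whether it precedes first intake, and what the contrast then estimates. State also how the two sucralose doses enter each model.

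The cost is SAP wording, to be fixed before unblinding, and one residual degree of freedom: with 144 participants, 144 − 3 = 141 becomes 144 − 4 = 140. No new data are needed, provided the *before* sample precedes first intake; the sponsor should confirm that first.

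### The repeated-measures ANOVA for the glucose tolerance curves has no sphericity correction and no rule for missed draws

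*SAP*

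**What the plan says.** The SAP's paragraph on the oral glucose tolerance curves names "an analysis of variance test for repeated measurements" and gives no more detail. It does not list factors, name an interaction, specify a covariance structure, mention sphericity, or say what happens to an incomplete curve.

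The Protocol (Materials and Methods) sets the sampling. Blood is drawn "at -15 (sucralose intake or placebo) and 0 (75 g glucose intake) as a base", then at "15, 30, 45, 60, 75, 90, 105, 120 and 180 minutes post-load glucose". That is 2 + 9 = 11 draws per test. After 10 weeks "a second CTOG (75g / 180 min) will be carried out" on the same schedule, so each volunteer has 22 draws.

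The principal outcome in the Protocol is the area under the insulin curve. In the SAP each area "will be assessed using the trapezium method", and for the change between the initial and final areas "an ANCOVA will be made, taking the BMI as a covariate".

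**The concern.** Classical repeated-measures ANOVA relies on sphericity: the difference between any two times must have the same variance for every pair of times. After a glucose load this is unlikely. Samples 15 minutes apart should resemble each other more than samples hours apart, and spread should be wider near the peak than at fasting. When sphericity fails, the uncorrected F test of arm by time rejects too often. That test asks whether sucralose changes the shape of the curve, and the plan measures six metabolic analytes.

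The same method needs complete curves. One missed draw among 11 removes the volunteer from that analysis, including from the arm main effect, which sphericity does not otherwise disturb.

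**Working it through.** **The plan's own figure.** The documents give no number for the repeated-measures analysis. The only figure to reproduce is the sample size for the two-group t test on insulin AUC, where "the sample size is 72 volunteers per group". With d = 0.419231264, the noncentrality is d × √(72/2) = 0.419231264 × 6 = 2.5154. With df = 142 and one-sided α = 0.05, the critical t is 1.6557 and the power is 0.8047. This matches the SAP.

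**Inputs for the curve analysis.** From the documents: k = 11 times, with nine gaps of 15 minutes and one of 60, and two groups of 72. Assumed, because the documents are silent: correlation between two times = ρ^(lag/15), with ρ from 0.3 to 0.9; SD either constant or in the ratio 1, 1, 3, 5, 6, 6, 6, 6, 5.5, 5, 3 along the curve.

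**Formulas.** With S the covariance matrix, C the centring matrix and A = CSC, ε = [tr(A)]² / [(k − 1) tr(A²)]. Sphericity means ε = 1. The uncorrected arm-by-time F uses 10 and 10 × 142 = 1,420 df. Greenhouse-Geisser multiplies both by the estimated ε. At ε = 0.356, for example, they become 3.56 and about 506.

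**Null simulation.** Rejection at nominal 5%, 4,000 trials per row, Monte Carlo error about ±0.7 to 1.0 points:

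| Pattern | ε | Uncorrected | Greenhouse-Geisser |
|---|---|---|---|
| Equal correlation 0.6 | 1.00 | 5.1% | 4.4% |
| Equal correlation 0.9 | 1.00 | 5.1% | 4.7% |
| Decaying, ρ = 0.3 | 0.89 | 6.5% | 5.2% |
| Decaying, ρ = 0.5 | 0.72 | 6.8% | 4.6% |
| Decaying, ρ = 0.7 | 0.54 | 9.3% | 4.7% |
| Decaying, ρ = 0.8 | 0.45 | 10.8% | 5.0% |
| Decaying, ρ = 0.9 | 0.36 | 11.1% | 4.9% |
| Decaying, ρ = 0.5, SD varies | 0.59 | 8.6% | 4.9% |
| Decaying, ρ = 0.7, SD varies | 0.48 | 10.3% | 4.5% |
| Decaying, ρ = 0.9, SD varies | 0.32 | 12.4% | 4.9% |

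Strong correlation alone does no harm: equal correlation of 0.9 leaves the test at 5.1%. The 60-minute gap is not the cause either. With 11 equally spaced times and ρ = 0.5, 0.7 and 0.9, the uncorrected test rejects 8.1%, 10.3% and 12.9%, against 6.8%, 9.3% and 11.1% on the Protocol's schedule.

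**Does a mixed model hold its level?** It depends on the specification.
- Unstructured covariance with a finite-sample F reference: 4.1–5.7% on complete data (4,000 trials per case). With 2% of draws missing it gives 3.8% at ρ = 0.7 and 5.5% at ρ = 0.9 (400 trials each, error about ±2 to 3 points).
- The same model with a Wald chi-square and no small-sample correction: 7.0–11.0%.
- A random-intercept model on complete balanced data has the same F as the uncorrected ANOVA, and so the same inflation.

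**Lost curves.** If each draw is missed independently with probability p (assumed), the share lost is 1 − (1 − p)^11 for one OGTT and 1 − (1 − p)^22 if both must be complete.

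| p | Lost, one OGTT | Retained of 144 | Lost, both needed | Retained of 144 |
|---|---|---|---|---|
| 1% | 10.5% | 129 | 19.8% | 115 |
| 2% | 19.9% | 115 | 35.9% | 92 |

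**The case against.** The SAP does not name an arm-by-time test and does not say that any F would go uncorrected. Many packages print a Greenhouse-Geisser line anyway. The sentence is also loosely worded. If its repeated factor were only the initial and final AUC, there would be two levels and sphericity would hold automatically. This stands to the extent that inflation is a possibility and not a certainty. It does not close the gap: with no line named, the choice between corrected and uncorrected output falls after the data are seen, and a printed correction recovers no dropped volunteer.

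The loss figures rest on an assumed missed-draw rate and on independent misses. If misses cluster in a few people, the same rate removes fewer volunteers. The larger pair, 20% and 36%, needs both tests to be complete in one analysis, which the SAP does not state. The calculation shows a loss of numbers under random misses; it does not show a biased selection.

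A reader might infer that the trial's main result is at risk. The documents do not support that. The principal outcome is one summary per OGTT, and an ANCOVA on its change involves no sphericity assumption. The AUC does have its own gap, since no rule covers a missing draw in the trapezium calculation, but that is a separate matter which a new curve model would not close.

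A reader might also infer that any mixed model cures the problem. The Wald and random-intercept results show otherwise.

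**Conclusion.** The point holds as a modest, conditional one about the curve-shape analysis. The plan names a method that needs sphericity and complete curves, and provides for neither.

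If the arm-by-time test is run uncorrected, its type I error lies anywhere from about 5% to about 12% for two arms of 72, depending on how far the covariance departs from sphericity. The top of that range needs a 15-minute correlation near 0.9 together with an SD that varies along the curve. The cause is non-sphericity, not strong correlation or unequal spacing as such.

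About 10% or 20% of volunteers would drop out of a single-OGTT analysis at 1% or 2% of draws missed independently. The correlations, SD pattern and missed-draw rates are all assumptions. The improvement is worth making because it is cheap, not because the principal comparison depends on it.

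**What to change.** Replace the ANOVA sentence with a linear mixed model fitted to each OGTT, using all available samples.
- **Fixed terms:** arm, categorical time, arm by time, baseline BMI, and the −15 minute value from the first OGTT only. At the second OGTT the −15 minute sample follows 10 weeks of daily intake, so adjusting for it could remove part of the chronic effect.
- **Covariance and df:** unstructured across times, with Kenward-Roger degrees of freedom. For the ten times from 0 to 180 minutes this means 10 × 11 / 2 = 55 parameters, so name a fallback structure in case the fit does not converge.
- **Missing pre-dose value:** state how it is handled, because a missing covariate would otherwise remove the curve again.

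If ANOVA is kept, make the Greenhouse-Geisser test the prespecified one. That restores the error rate (4.5–5.2% in the decaying-correlation cases) but not the lost volunteers.

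The cost is a few lines of SAP text and slightly more analysis work, with no extra data. The mixed model relies on draws being missing at random. A separate line should say how the trapezium AUC is computed when a draw is missing.
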